The effectiveness and safety of the early follicular phase full-dose down-regulation protocol for controlled ovarian hyperstimulation: a randomized, paralleled controlled, multicenter trial

2018-12-29

Background

Since the first “tube baby”, Louise Brown, was born in the United Kingdom in 1978, many infertile couples have been benefitted from in vitro fertilization and embryo transfer (IVF-ET) and intracytoplasmic sperm injection (ICSI). It is reported that there are over 5 million babies born with the help of assisted reproductive technology (ART). According to the 2015 national data published by Human Fertility and Embryology Authority (HFEA, 48,147 women received 61,726 IVF/ICSI cycles and gave birth to 17,041 newborns [1]. In the United States, 169,602 IVF/ICSI cycles were performed in 2014 and 68,791 tubal babies were born [2]. China has a huge population base, and therefore has a substantial number of infertile couples. Although a late starter, China is developing rapidly in ART and playing a more and more important role in the area of reproductive medicine.

In spite of the continuous development in ART, so far, the overall success rate of IVF/ICSI is still hovering around 25-40%. The live birth rate per stimulated cycle is 25.6% in the UK in 2015, fluctuating from 1.9% in women aged 45 and elder to 32.2% in women younger than 35 years old [1]. The IVF/ICSI success rate in 2014 in the US is similar [2]. In China, according to the data submitted by 115 reproductive medicine centers on the ART data reporting system developed by Chinese Society of Reproductive Medicine, the delivery rate is about 40% [3]. Hence, there is much room for improvement regarding the live birth rate of IVF/ICSI, which is of great significance to infertile couples.

There are many factors influencing the success rate of IVF/ICSI, e.g. the infertile couples' age, the controlled ovarian hyperstimulation (COH) protocol, the quality and number of embryos for transferring, the endometrium and luteal phase support protocol, etc. Among them, an appropriate COH protocol is directly associated with the number of oocyte retrieved, as well as the number and quality of embryos, which exert an important influence on the success rate of IVF/ICSI. The luteal phase pituitary down-regulation protocol is one of the most widely used COH protocols in clinical practice, particularly in China. In this protocol, gonadotropin releasing hormone agonist (GnRHa) administered in the previous luteal phase induces a state of down regulation of the pituitary gland via competitive occupying and further exhausting the GnRH receptors in the pituitary, which inhibits the endogenous luteinizing hormone (LH) peak and avoid spontaneous ovulation, decreasing the cycle cancellation rate. But the classic down-regulation protocol may lead to an increased incidence of ovarian hyperstimulation syndrome (OHSS), as well as a negative impact on endometrial receptivity due to the progesterone elevation after multiple oocytes development [4]. The coping strategy is to freeze all the embryos and transfer in the next cycle. Though avoiding the above-mentioned adverse effects, such strategy increases the time to pregnancy (TTP) and therefore results in certain psychological and economic burdens for infertile couples.

In recent years, some Chinese researches applied the early follicular full-dose down-regulation protocol that is always performed to women with endometriosis to a more general IVF/ICSI population and found a clinical pregnancy rate of 64% in the fresh embryo transfer cycle, much higher than that of the luteal phase down-regulation protocol [5-10]. The possible mechanism is that it may improve the down regulation of LH and the endometrial receptivity, therefore having a

better control of LH during COH, increasing the endometrial thickness on hCG day, as well as the embryo implantation rate and clinical pregnancy rate. Furthermore, since this protocol decrease the risk of progesterone elevation on hCG day, it increases the fresh embryo transfer rate and shortens TTP.

Given most studies regarding the effectiveness and safety of the early follicular phase full-dose down-regulation protocol are retrospective studies, the results may be biased by several confounding factors. Therefore, we would like to conduct a multicenter, randomized controlled trial to compare the pregnancy outcome and safety between the early follicular phase full-dose down-regulation COH protocol and the luteal phase down-regulation protocol.

Methods/Design

We will perform the multicenter, randomized controlled trial in 14 reproductive medicine centers all over mainland China. Included patients will be distributed in a 1:1 ratio to the intervention (early follicular phase full-dose down-regulation) group and the control (mid-luteal phase down-regulation) group. Their live birth rate of fresh embryo transfer and other secondary outcomes will be compared. This study has been approved by the institutional review boards at all study sites. Each participant will sign the consent form before inclusion. Reporting of the study results will follow the 2010 CONSORT statement [11].

Inclusion criteria

The following are the inclusion criteria for this study:

1. Women aged between 20 to 38 years old and with a history of infertility (fail to get pregnant after over one year's regular, unprotected sex), who receive IVF/ICSI for one of the following reasons:
 - ① Tubal factor: e.g. peritubal adhesions, tubal obstruction, etc.. Patients with hydrosalpinx can be enrolled after salpingectomy or tubal ligation;
 - ② Male factor: e.g. oligospermia, asthenozoospermia, teratozoospermia, etc.;
 - ③ Unexplained infertility: patients with a history of infertility more than 1 year but with no specific cause for infertility (ovulation, tubal, endometrial and male factor), or still not get pregnant after the above-mentioned causes being removed.
2. Women with a normal ovarian reserve according to: ① basal steroid hormone on day 2-4 of menstrual cycle: basal FSH≤10mIU/ml, estradiol (E2) <50pg/ml; ② anti-Müllerian hormone (AMH)≥1.1ng/ml; ③ antral follicle count (AFC) ≥7;
3. Women who start their first IVF/ICSI cycle;
4. Women who met the above-mentioned criteria and have given the informed consent.

Exclusion criteria

1. Women with a negative reproductive history, including a history of:
 - ① recurrent miscarriage: women with twice and more than twice spontaneous miscarriage, missed abortion, biochemical pregnancies, etc.;
 - ② fetal malformation or chromosomal abnormalities;

- ③ intrauterine death.
- 2. Women with a history of one side adnexectomy;
- 3. Women with a poor ovarian response or diminished ovarian reserve (based on Bologna' criteria);
- 4. Women with ovulation dysfunction;
- 5. Women with PCOS (based on Rotterdam's criteria);
- 6. Women with endometriosis;
- 7. Women with the following uterine abnormalities: uterine malformation (unicornuate uterus, uterus bicornis, uterus duplex, mediastinum uterus), adenomyosis, submucosa myoma, intrauterine adhesion;
- 8. Chromosomal abnormality for either or both of the couple;
- 9. Women with contraindications for ART or pregnancy: uncontrolled diabetes mellitus, cardiac disease, undiagnosed liver and/or renal function, vaginal bleeding, suspected or a past history of cervical cancer, endometrial cancer, breast cancer, and a history of deep venous thrombosis, pulmonary embolism, stroke, etc.;
- 10. Women who are enrolled in other clinical trials.

Randomization

After the evaluation, patients met the eligible criteria will be informed, sign the consent form and be included in this study. We will randomly assign women (1:1) to the two groups, using a central randomization system with block sizes of 4 to 6 (changing constantly) and setting hospital as a stratification factor. The researchers (physicians, nurses and embryologists) and patients are not blinded due to the nature of both interventions while the data analysts are blinded.

Interventions

Pituitary down-regulation and controlled ovarian hyperstimulation(COH)

1. *Pituitary down-regulation and starting dose determination*

After inclusion and randomization, qualified participants will be in either intervention or control group and receive one of the following treatments:

1) *Intervention group* (early follicular phase full-dose down-regulation group)

Patients have an injection of 3.75mg long-acting triptorelin acetate (Dipherelin®, IPSEN, France) on the 1st-4th day of menstrual cycle and receive the endocrinology and ultrasound examinations 28-42 days thereafter. If complete pituitary down-regulation is achieved (endometrial thickness≤5mm, basal FSH≤5mIU/mL, LH≤5mIU/mL, E2≤50pg/mL) and the diameter of follicles between 4-6mm under ultrasound, a supplementation of recombinant FSH (Gonal-F®, Merck, Switzerland) will be given according to the participants' BMI (18≤BMI≤22, starting dose 112.5IU/d; 22<BMI≤25, starting dose 150IU/d.

2) *Control group* (luteal phase long down-regulation group)

Patients have an injection of short-acting triptorelin acetate (Decapeptyl®, Ferring, Germany) 0.1mg every day, 10-12 days before the menstruation and receive the endocrinology and ultrasound examinations 14-21 days thereafter. If complete pituitary down-regulation is achieved (endometrial thickness≤5mm, basal FSH≤5mIU/mL, LH≤5mIU/mL, E2≤50pg/mL) and the diameter of follicles between 4-6mm under ultrasound,

a supplementation of recombinant FSH (Gonal-F®, Merck, Switzerland) will be given according to the participants' BMI ($18 \leq \text{BMI} \leq 22$, starting dose 112.5IU/d; $22 < \text{BMI} \leq 25$, starting dose 150IU/d).

2. *Ovarian response monitoring and gonadotropin dose adjustment:* 4 days after the daily injection of rFSH, the physician will perform ultrasound to monitor the follicular growth, measure the serum hormone level and adjust the dose of exogenous gonadotropins accordingly.

Trigger and oocyte retrieval

1. *hCG trigger for final oocyte maturation:* When the desired follicle size is reached (at least one follicle ≥ 19 mm or two follicles ≥ 18 mm or three follicles ≥ 17 mm), 250 μ g recombinant human chorionic gonadotropin (HCG) (Luveris®, Merck, Switzerland) will be administered subcutaneously.
2. *Oocyte retrieval:* Oocyte retrieval will be performed transvaginally 36-38 hours after pre-ovulatory hCG injection under ultrasound monitoring.
3. *In vitro fertilization and embryo culture:* Oocyte retrieved will be cultured in vitro for 3-6h before being fertilized via IVF or ICSI. Two top-quality Day 3 cleavage embryos will be transferred 72h after retrieval. If more than 15 oocytes are retrieved, the participant should receive ultrasound examination on the day of embryo transfer. For those complaining abdominal or stomach distension, with an ovary ≥ 7 cm in diameter, estradiol ≥ 4500 pg/ml, there is a high risk of developing moderate or severe OHSS, and all the embryos should be frozen.

Embryo transfer and luteal phase support

Patients will receive luteal phase support with intramuscular progesterone (60mg/day) since the day of oocyte retrieval. On day 3 after oocyte retrieval, two top quality cleavage-stage embryos will be transferred via a catheter under transabdominal ultrasound guidance. The patients will lie in bed for 15 minutes after the procedure. After embryo transfer, 8% progesterone sustained-releasing vaginal gel (Crinone®, Merck, Switzerland) 90mg and dydrogesterone (Duphaston®, AbbottBiologicals, Netherlands) 20mg every day will be used as luteal phase support, continuing for at least 2 weeks. For those who get pregnancy, luteal phase support will be continued to 10 weeks of gestation. The dosage adjustment will be determined by physicians of each study site according to their personal experience.

Pregnancy evaluation and follow-up

All the information will be recorded in our follow-up forms designed specifically for each follow-up visit.

1. *Biochemical determination:* 14 ± 4 days after embryo transfer, serum β -hCG will be tested to determine pregnancy.
2. *Clinical pregnancy determination:* 28 ± 4 days after embryo transfer, a transvaginal ultrasound scan will be performed to confirm the presence of fetal sac, yolk sac and fetal heart.
3. *Ongoing pregnancy determination:* A transvaginal ultrasound scan will be performed at 10-12 weeks of gestation to confirm ongoing pregnancy. The presence of first-trimester pregnancy complications (e.g. OHSS, ectopic pregnancy, miscarriage etc.) will be registered according to the participant's medical record and a telephone follow-up.
4. *28 weeks of gestation:* A telephone follow-up will be conducted to collect the information regarding the second-trimester complications, e.g. pre-eclampsia, gestational diabetes,

prenatal diagnosis, miscarriage, etc.

5. 37 weeks of gestation: A telephone follow-up will be conducted to collect the information regarding the third-trimester complications, e.g. pre-eclampsia, gestational diabetes, preterm birth, etc.
6. *Delivery information:* A telephone follow-up will be made to collect delivery information including gestational age, delivery mode, delivery complications and infant information such as birth weight, any birth defect, etc.
7. *Postpartum information:* Postpartum information includes complications of both the mother and the infant, which will be collected 6 weeks after delivery.

For those not receiving a fresh embryo transfer (e.g. due to OHSS), and those not achieving live birth and with surplus cryopreserved embryos, the outcome of frozen-thawed embryo transfer cycles will be followed up and recorded as well.

Outcome measurements

Primary outcome

The primary outcome of this study is live birth rate per transferred cycle, defined as delivery of any viable infant ≥ 28 gestational weeks divided by all transferred cycles.

Secondary outcomes

Secondary effectiveness endpoints will include implantation rate, biochemical pregnancy, clinical pregnancy and ongoing pregnancy. *Biochemical pregnancy* will be achieved if serum β -hCG ≥ 10 U/L. *Clinical pregnancy* is defined as the presence of an intrauterine gestational sac 28 ± 4 days after embryo transfer. Ongoing pregnancy is defined as a viable pregnancy at 10-12 gestational week. The safety endpoints will include moderate and severe OHSS, pregnancy loss, pregnancy complications, neonatal birth weight and adverse fetal outcomes (e.g. malformation, intrauterine fetal death, etc.)

Statistical analysis

Sample size and power calculation

Sample size will be calculated based on superiority test. The significance level will be set at $\alpha = 0.05$ and the statistical power will be set as $1 - \beta = 0.80$. The reported live birth rate is about 30%, while the live birth rate of the prolonged protocol is predicted to be around 40% based on previous retrospective studies. We set the delta value as 6%, and the ratio between groups will be 1:1; therefore, the sample size of each group is 851. Taking into consideration a drop rate of 10%, we expect to ultimately have a total of 1892 enrollees, with 946 participants in each group.

Statistical analysis method

1. Statistical description: We will adopt descriptive statistical analysis to summarize the participants' demographic characteristics, physical examination, laboratory tests, other health information and the outcome indicators. The continuous variables will be described with means and standard deviation (or median and interquartile range), while the categorical variable will be described with frequency and percentage. The proportion of drop-off cases will be calculated and analyzed.
2. Comparable analysis It will be used to compare the demographic and other baseline characteristics to make sure the comparability of the two groups. If the continuous variables follow the normal distribution, t test will be performed; if not, the rank sum

test or a normal transformation will be performed. For the categorical variables, chi-square test or Fisher's exact test will be performed.

3. Statistical analysis for the outcome measures Between-group differences for categorical and continuous outcome variables will be assessed by logistic regression and linear regression, respectively.
4. Safety analysis: Adverse events and reaction will be listed and analyzed using the chi-square test.
5. The analysis for the primary outcome and important outcome measurements will be based on both the intention-to-treat analysis and per-protocol analysis. The results of these two analyses will be compared in the final analysis.

Reference

- [1] The United Kingdom national data. Human Fertility and Embryology Authority. 2015
- [2] The United States national assisted reproductive technology(ART) data. Centers for Disease Control and Prevention.2015
- [3] Chinese Reproductive Medicine Society national assisted reproductive technology (ART) data. 2015
- [4] L Hu, Y Sun. The impact of various controlled ovarian hyperstimulation (COS) protocols on the outcome of in vitro fertilization and embryo transfer (IVF-ET). *Journal of Practical Obstetrics and Gynecology*. 2014;30(10):723-725.
- [5] Y Hu, T Ding, Y Zhao, Q Wu. The comparison of the birth outcome of in vitro fertilization and embryo transfer (IVF-ET) after two different down-regulation protocols. *Maternal and Child Health Care of China*.2017;32(4):808-810.
- [6] D Xu, Q Wu. The comparison of the application of ultra-long down-regulation protocol and antagonist protocol in in vitro fertilization and embryo transfer (IVF-ET). *Jiangxi Medical Journal*. 2015;50(1):13-15.
- [7] Q Su, Q Wu, L Tian, Y Li. The clinical analysis of different controlled ovarian hyperstimulation (COS) protocols in in vitro fertilization and embryo transfer (IVF-ET). *Jiangxi Medical Journal*. 2014;49(8):723-725.
- [8] Y Li, Q Wu, Y Yi. The impact of the follicular phase ultra-long long down-regulation protocol on PCOS patients' outcome after in vitro fertilization and embryo transfer (IVF-ET). *Jiangxi Medical Journal*. 2014;49(2):117-120.

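### Frozen-transfer outcomes are recorded but, if the primary outcome is fresh-only, no prespecified outcome uses them, and live birth is not compared across all randomised women

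*Combined protocol and SAP*

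**What the plan says.** All references are to the combined protocol and SAP.

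- **Background.** Freezing all embryos is said to lengthen time to pregnancy. After describing LH control and endometrial receptivity as the possible mechanism, the text adds that the intervention lowers the risk of progesterone elevation and so "it increases the fresh embryo transfer rate and shortens TTP".
- **Methods/Design, opening paragraph.** "Their live birth rate of fresh embryo transfer and other secondary outcomes will be compared".
- **Trigger and oocyte retrieval, item 3.** Women judged at high risk of moderate or severe OHSS have all embryos frozen. The rule refers to reported symptoms, ovarian size and estradiol. Under Randomization, treating staff and patients are not blinded.
- **Pregnancy evaluation and follow-up, final paragraph.** Two groups are covered: women who had no fresh transfer, and women without a live birth who still have frozen embryos. In both groups, "the outcome of frozen-thawed embryo transfer cycles will be followed up and recorded as well". No duration or visit schedule is given for this follow-up.
- **Primary outcome.** "live birth rate per transferred cycle, defined as delivery of any viable infant" at 28 weeks or later, "divided by all transferred cycles". The word fresh does not appear here.
- **Secondary outcomes.** "Secondary effectiveness endpoints will include implantation rate, biochemical pregnancy, clinical pregnancy and ongoing pregnancy". The safety outcomes are OHSS, pregnancy loss, pregnancy complications, birth weight and adverse fetal outcomes.
- **Statistical analysis method.** Logistic regression, linear regression and chi-square tests are named, with intention-to-treat and per-protocol analyses. No time-to-event method is named.

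**The concern.** The decision to freeze all embryos comes after randomisation and may differ between the arms; the Background expects that it will. A woman without a fresh transfer is outside a denominator of fresh transfers, so the primary comparison is not between the groups as randomised. The data that would bring her back in are collected, but on the fresh-only reading they have no assigned use.

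Changing the denominator alone does not settle the matter. Per fresh transfer, these women are absent. Per randomised woman with fresh transfers only, each counts as a failure even if a frozen embryo later gives a live birth. At stake is whether the trial can report, from a prespecified analysis, that one protocol leads to more women having a baby, or that similar numbers have a baby at a different time.

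**Working it through.** **Inputs.** From the plan: live birth about 30% in control and around 40% predicted with the intervention, a delta of 6 points, and 1892 women in total (851/0.9 = 945.6, rounded up to 946 per arm; 946 × 2 = 1892). The plan gives no fresh-transfer or freeze-all rate, so those below are assumptions.

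**Step 1: is any outcome attached to the frozen-cycle data?** The answer depends on two passages. Methods/Design says the compared rate is that of fresh transfer. The Primary outcome definition counts every transferred cycle, which read literally admits frozen ones. On the first reading, no listed outcome uses the frozen data. On the second, a woman can contribute several cycles, and the plan gives no rule for this. On either reading, cumulative live birth per woman, fresh-transfer rate and time to pregnancy are not listed.

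**Step 2: how many women could be outside a fresh-transfer denominator?** Assume that 60 to 90% of women have a fresh transfer. Then 1892 × 0.10 = 189 to 1892 × 0.40 = 757 women are outside it.

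**Step 3: what does each endpoint show when live birth per transfer is the same in both arms?** Let L be live birth per fresh transfer and G the excess of freeze-all in control.

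- Per transfer: L − L = 0 for any G.
- Fresh-only, per randomised woman: G × L.

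| G (assumed) | L = 30% | L = 40% |
|---|---|---|
| 5 points | 1.5 | 2.0 |
| 10 points | 3.0 | 4.0 |
| 15 points | 4.5 | 6.0 |

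Only the most extreme cell equals the plan's 6-point delta.

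**Step 4: can either separate more babies from earlier babies?** Take fresh transfer in 70% of control and 80% of intervention women, with L = 30%. Per transfer the difference is 0. Fresh-only per randomised woman, it is 0.80 × 0.30 − 0.70 × 0.30 = 24% − 21% = 3 points. Now suppose every remaining woman has one frozen transfer with live birth rate F. Live birth after each woman's first transfer then differs by

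(0.80 × 0.30 + 0.20 × F) − (0.70 × 0.30 + 0.30 × F) = 0.10 × (0.30 − F).

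- F = 0: 3 points in favour of the intervention (more babies).
- F = 30%: 0 (the same number of babies, later for the frozen group).
- F = 40%: 1 point in favour of control.

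The two fresh-only endpoints show 0 and 3 points in all three cases. Only the frozen-cycle outcomes tell the cases apart.

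**Step 5: could cumulative live birth carry a power claim?** With the usual two-proportion formula, two-sided 0.05, 80% power and assumed control rates of 40 to 60%, a 6-point difference needs 1016 to 1086 women per arm before dropout. With 851 per arm, power for 6 points is 70 to 73%, and the detectable difference is about 6.6 to 6.8 points.

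**The case against.** A fresh-cycle endpoint is coherent for a hypothesis about endometrial receptivity, which is the Background's leading mechanism. The stated aim is pregnancy outcome and safety. More fresh transfers and shorter time to pregnancy come second, as rationale and not as trial hypotheses. This stands: omitting the extra outcomes does not invalidate the comparison the plan sets out.

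The plan also promises an intention-to-treat analysis, which might be taken to restore all randomised women. It does not restate the denominator, however. If the endpoint stays fresh-only, all randomised women could enter only by counting freeze-all as failure, which is the second endpoint in the working.

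Three stronger inferences are tempting, and the documents do not support them.

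- *The trial cannot test its Background claims.* Fresh-transfer rate needs only each woman's transfer status, and time to pregnancy might be analysed post hoc if dates are kept. What is missing is prespecification.
- *The fresh endpoint mishandles every woman followed into frozen cycles.* A woman whose fresh transfer failed is correctly a failure for that endpoint. She matters here only for cumulative live birth.
- *The primary result is biased by up to 6 points.* Those figures belong to a per-randomised, fresh-only rate that the plan does not define. On equal live birth per transfer, the plan's own endpoint gives 0. Bias from who is left in the per-transfer denominator is possible but cannot be sized from the documents.

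Freeze-all is also not left wholly to an unblinded physician, since the rule includes measured thresholds alongside symptoms.

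**Conclusion.** The point holds as a gap in prespecification, and it should be closed before the data are analysed. If the primary outcome is fresh-only, the frozen-cycle data have no planned use. The plan then has no prespecified comparison of live birth across all randomised women, of fresh-transfer rate, or of time to pregnancy. The statement that no outcome uses the frozen data depends on the Methods/Design wording prevailing over the literal Primary outcome definition, so those two places must be reconciled first.

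The size is illustrative: a difference of 0 per transfer, against 1.5 to 6 points per randomised woman. This assumes equal live birth per transfer of 30 to 40% and freeze-all gaps of 5 to 15 points, and the plan gives no freeze-all rates.

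**What to change.** 1. State whether the primary outcome's transferred cycles are fresh only, and make Methods/Design and Primary outcome agree. If frozen cycles are admitted, state how repeated cycles from one woman are handled.
2. Add three secondary outcomes:
   - **Fresh-transfer rate per woman randomised.**
   - **Cumulative live birth per woman randomised:** at least one live birth, by the plan's definition, from fresh or frozen transfer of embryos from the first stimulated cycle. Count transfers over the same fixed window from randomisation in both arms (for example 12 months). Analyse by hospital-adjusted logistic regression.
   - **Time from randomisation to the first pregnancy from those embryos that ends in live birth:** Kaplan-Meier curves and hospital-stratified Cox regression. Women with no such pregnancy, including those who use up their embryos, stay at risk until the end of the window; dropping them earlier would make censoring depend on failure. State the rule for loss to follow-up. The clock should start at randomisation because the waits before examination (28-42 and 14-21 days) run from injections given at different points of the cycle.
3. Label these outcomes supportive, and either make no power claim for them or state a multiplicity rule.

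The cost is SAP wording and three analyses. Frozen-cycle follow-up is already intended, but its length is not stated. Transfer and pregnancy dates must be captured, late transfers must be followed to delivery, and these results will come after the fresh-cycle result.

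### The primary live birth rate is counted per transferred cycle, a denominator formed after randomisation that the protocol expects treatment to change, and the promised ITT analysis gives no rule for women without a transfer

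*Combined protocol and SAP*

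**What the plan says.** **Endpoint.** Under Outcome measurements, Primary outcome: "The primary outcome of this study is live birth rate per transferred cycle". The numerator is delivery of a viable infant at 28 weeks or later; the denominator is every transferred cycle.

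**Timing of randomisation.** Under Interventions: "After inclusion and randomization, qualified participants will be in either intervention or control group". Down-regulation, stimulation, retrieval and transfer all follow.

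**Routes to no fresh transfer.** In both arms the start of FSH is made conditional: "If complete pituitary down-regulation is achieved". Under Trigger and oocyte retrieval, item 3, women meeting a stated description are treated as follows: "there is a high risk of developing moderate or severe OHSS, and all the embryos should be frozen".

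**Expected difference between arms.** The Background lists adverse effects of the classic luteal-phase protocol and continues: "The coping strategy is to freeze all the embryos and transfer in the next cycle". Of the intervention it says that "it increases the fresh embryo transfer rate and shortens TTP".

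**Which transfers count.** Methods/Design names the live birth rate of fresh embryo transfer as the comparison. The primary outcome refers to all transferred cycles without the word fresh. Just before it, the follow-up section says, for women without a fresh transfer and for those without a live birth who have surplus frozen embryos, that "the outcome of frozen-thawed embryo transfer cycles will be followed up and recorded as well".

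**Analysis sets.** Statistical analysis method, item 5, promises intention-to-treat and per-protocol analyses of the primary outcome. Neither population is defined.

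**The concern.** Randomisation makes the two groups of randomised women comparable. It does not do so for the women in each arm who reach transfer, if the treatment affects who reaches it, and the protocol's own rationale says it does. A per-transfer rate then mixes two effects: the chance of live birth once embryos are transferred, and the selection of women who get that far. On the fresh-transfer reading, a woman with no fresh transfer is in neither the numerator nor the denominator.

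The ITT commitment does not settle this. An ITT analysis of transferred cycles and an ITT analysis of randomised women are different analyses, and the text allows either. If frozen cycles count, the expected difference in fresh transfer matters less, but one woman can contribute several cycles, and the planned logistic regression has no stated provision for that.

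At stake is the analysis that decides superiority. As written, the primary result would not say directly which protocol gives a woman starting treatment more live births from that cycle, and the denominator could be chosen after the data are seen.

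**Working it through.** **Inputs from the documents** (Sample size and power calculation): live birth 30% (control) and 40% (intervention), delta 6%, alpha 0.05, power 80%, 851 per group, 10% drop rate, 946 per group. The test is taken as two-sided; the text does not say. Fresh transfer rates are not given, so all of those below are **assumptions**.

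**The plan's own figure.** The drop-out step reproduces: 851/0.90 = 945.6, so 946 per group and 1892 in total. The 851 does not follow from the stated rates. 30% v 36% needs 963 per group and 30% v 40% needs 356 (two-sided, 80% power). That is a separate matter; 946 randomised per group is used here.

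**Relation between the two rates.** With one fresh cycle per woman and transfer probability *t*:

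- live birth per woman = *t* × live birth per transfer
- risk ratio per woman = risk ratio per transfer × (*t* intervention / *t* control)

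**1. Predicted 30% v 40% per transfer** (difference 10 points, ratio 1.33):

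| Transferred, control v intervention | Per-woman rates | Difference | Ratio |
|---|---|---|---|
| 70% v 75% | 21.0% v 30.0% | 9.0 points | 1.43 |
| 80% v 82% | 24.0% v 32.8% | 8.8 points | 1.37 |
| 80% v 85% | 24.0% v 34.0% | 10.0 points | 1.42 |
| 80% v 90% | 24.0% v 36.0% | 12.0 points | 1.50 |

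If the intervention raises transfer, the per-transfer ratio understates the per-woman ratio. The absolute difference may be overstated, equal or understated. The two differences agree when *t* intervention = (0.10 + 0.30 × *t* control)/0.40, which is 77.5%, 85% and 92.5% for a control transfer rate of 70%, 80% and 90%.

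**2. Power.** Pooled two-proportion z test: power = Φ[(difference − 1.96 × SE₀)/SE₁], where SE₀ uses the pooled rate and SE₁ the separate rates.

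- 30% v 40%, 70% v 75% transferred. Per transfer (662 v 710 women): 97%. Per woman (21% v 30%, 946 each): 99%.
- 30% v 36%, 80% v 85% transferred. Per transfer (757 v 804): SE₀ = 0.0238, SE₁ = 0.0237, power 71%. Per woman (24.0% v 30.6%, 946 each): SE₀ = 0.0205, SE₁ = 0.0204, power 90%.

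**3. Limiting case in the direction the Background expects.** 35% per transfer in both arms, 75% (control) v 85% (intervention) transferred. Per woman: 0.35 × 0.75 = 26.25% v 0.35 × 0.85 = 29.75%, a gain of 3.5 points. Per transfer the difference is zero. In 400,000 simulated trials the test favoured the intervention 2.5% of the time per transfer and 39% per woman.

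**4. Limiting case in the opposite direction.** Equal 25.5% per woman, with control 85% and intervention 75% transferred. Per transfer: 0.255/0.85 = 30% v 0.255/0.75 = 34%. The per-transfer test then declares superiority about 38% of the time although the per-woman rates are equal. The conclusion does not rest on this case.

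**5. Power cost of the per-woman denominator if transfer is equal in both arms:**

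| Transferred, both arms | 30% v 36%: per transfer | 30% v 36%: per woman | 30% v 40%: per transfer | 30% v 40%: per woman |
|---|---|---|---|---|
| 90% | 75% | 73% | 99% | 99% |
| 80% | 70% | 66% | 98% | 97% |
| 70% | 64% | 58% | 97% | 94% |

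With everyone transferred and analysed, 946 per group gives 79.3% for 30% v 36%, so part of the shortfall from 80% comes from the sample size itself.

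**The case against.** The strongest reply is that, in the direction the protocol expects, the endpoint is conservative. If the intervention raises fresh transfer, a per-transfer ratio above 1 implies a larger per-woman ratio, and false superiority needs the opposite imbalance. This stands. So does the point that at the predicted 30% v 40% the choice would hardly change the chance of success. The expected harm is lost sensitivity and an estimate that answers a different question.

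The 71% v 90% contrast is not a pure denominator effect: the per-woman alternative (24.0% v 30.6%) includes an assumed transfer benefit. That is correct, and with equal transfer the per-woman analysis has slightly lower power.

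The expected imbalance is a Background statement resting on less progesterone elevation, whereas the only freeze-all rule in the treatment section concerns OHSS risk. PCOS is also excluded. This makes the size of the imbalance uncertain; it does not make transfer a pre-randomisation event.

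The fresh v all-cycles wording can be read naturally as fresh only, with frozen outcomes recorded in addition. That is reasonable, but it should be stated, and it leaves the ITT denominator open.

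Finally, ITT in its ordinary meaning covers all randomised women. If that is intended, it conflicts with an endpoint divided by transferred cycles, and the plan does not say which governs. The flow diagram is not available here; it might list transfers by arm, but it would not set the analysis rule.

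**Conclusion.** The concern holds and must be fixed. The primary endpoint as written conditions on an event after randomisation that the protocol expects to differ by arm, and the undefined ITT analysis does not resolve it. This follows from the text alone and needs no assumed rate.

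The size and direction of the bias cannot be determined from the documents. Over the assumed transfer rates, the effect runs from negligible for the decision (97% v 99% power at 30% v 40%) to material at a 6-point effect (71% v 90%). In the limiting case a 3.5-point gain per woman is invisible per transfer. These figures assume one fresh cycle per woman and a two-sided 0.05 test. Whichever way the numbers fall, the plan leaves open which denominator decides superiority.

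**What to change.** **Necessary.** Define the primary ITT analysis with all randomised women, as allocated, in the denominator and one outcome per woman. State how a woman without a transfer counts. State that this analysis decides superiority. Make Methods/Design and the Primary outcome section agree on whether frozen transfers count.

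**Numerator.** Preferred: live birth at 28 weeks or later from the fresh transfer of the randomised cycle, with no fresh transfer counted as no live birth from that cycle. Cumulative live birth per randomised woman over a stated period is an acceptable alternative; the choice is the sponsor's. If the fresh-cycle numerator is used, also report cumulative live birth per randomised woman from the frozen-cycle outcomes already being recorded, so that freeze-all women are not judged only as failures.

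**Supportive.** Keep live birth per transfer and the per-protocol analysis. Report the proportion reaching fresh transfer by arm, with reasons.

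**Cost.** Mainly wording and a power statement on the new denominator. With equal transfer of 90%, 80% or 70% (assumed), the denominator costs about 2, 4 or 6 points of power at 30% v 36%; at 30% v 40% per-woman power stays at 94% or more. The 10% drop allowance may have been meant to cover non-transfer; the text should say. Women with neither a transfer nor frozen embryos have no described follow-up, so their outcome status should be confirmed, which matters mainly for the cumulative outcome. This change does not by itself require more enrolment and does not alter treatment.
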